10.5.3 Toxicity Follow-up

Follow-up for toxicities

All participants will be followed for safety until 30 days after the last dose of neratinib and capmatinib. Participants whose treatment is temporarily interrupted or permanently discontinued due to an AE or abnormal laboratory value must be followed until resolution or stabilization of the event, whichever comes first, including all study assessments appropriate to monitor the event.

An unscheduled assessment should be performed in all cases below where toxicity monitoring is recommended more frequently than defined by the schedule of assessments. Subsequent monitoring must be performed as per the regular visit schedule.

Table 16. Follow-up Evaluations for Selected Toxicities*

TOXICITY	FOLLOW-UP EVALUATION
HEMATOLOGICAL	
Febrile neutropenia,	Test weekly (or more frequently if clinically indicated) until \leq CTCAE grade 2.
Neutropenia \geq CTCAE grade 3	
Thrombocytopenia \geq CTCAE grade 3	Perform physical exam for check on bruising in case of major thrombocytopenia.
Anemia \geq CTCAE grade 3	
RENAL	
Serum creatinine \geq CTCAE grade 2	Test weekly (or more frequently if clinically indicated) until \leq CTCAE grade 1 or baseline. Participants will be instructed to increase hydration until resolution to \leq CTCAE grade 1 or baseline.
HEPATIC	
Isolated total bilirubin elevation	Total bilirubin CTCAE Grade 1: Monitor LFTs per protocol or more frequently if clinically indicated Total bilirubin CTCAE Grade 2:

TOXICITY	FOLLOW-UP EVALUATION
	
Weekly monitoring of LFTs, or more frequently if clinically indicated, until resolved to $\leq 1.5 \times$ ULN
 
Total bilirubin CTCAE Grade 3:
 
Weekly monitoring of LFTs, or more frequently if clinically indicated, until resolved to $\leq 1.5 \times$ ULN. If resolved in > 7 days, after discontinuing the participant from capmatinib permanently, the participant should be monitored weekly (including LFTs), or more frequently if clinically indicated, until total bilirubin have resolved to baseline or stabilization over 4 weeks
 
Total bilirubin CTCAE Grade 4:
 
After discontinuing the participant from capmatinib permanently, the participant should be monitored weekly (including LFTs), or more frequently if clinically indicated, until total bilirubin have resolved to baseline or stabilization over 4 weeks

Isolated AST/ALT elevation	
AST/ALT CTCAE Grade 2 elevation:
 
For participants with baseline value $\leq 3.0 \times$ ULN: repeat LFTs as soon as possible, preferably within 48-72 hr from awareness of the abnormal results; if abnormal lab values are confirmed upon the repeat test, then monitor LFTs weekly, or more frequently if clinically indicated, until resolved to $\leq 3.0 \times$ ULN
 
For participants with baseline value $> 3.0 \times$ ULN: monitor LFTs per protocol or more frequently if clinically indicated
 
AST/ALT CTCAE Grade 3 elevation:
 
For AST/ALT elevation $> 5.0 - 10.0 \times$ ULN:
 
 For participants with baseline value $\leq 3.0 \times$ ULN: repeat LFTs as soon as possible, preferably within 48-72 hr from awareness of the abnormal results; monitor LFTs weekly, or more frequently if clinically indicated, until resolved to $\leq 3.0 \times$ ULN For participants with baseline value $> 3.0 \times$ ULN: repeat LFTs as soon as possible, preferably within 48-72 hr from awareness of the abnormal results; if abnormal lab values are confirmed upon the repeat test, then monitor LFTs, weekly, or more frequently if clinically indicated, until resolved to $\leq 5.0 \times$ ULN 
For AST/ALT elevation $> 10.0 - 20.0 \times$ ULN:
 
 Repeat LFTs as soon as possible, preferably within 48-72 hr from awareness of the abnormal results; monitor LFTs weekly, or more frequently if clinically indicated, until resolved to \leq baseline

TOXICITY	FOLLOW-UP EVALUATION
	
AST/ALT CTCAE Grade 4 elevation:
 
Repeat LFTs as soon as possible, preferably within 48-72 hr from awareness of the abnormal results; monitor LFTs weekly, or more frequently if clinically indicated, until resolved to baseline or stabilization over 4 weeks.

Combined elevations in ALT and/or AST with concurrent total bilirubin increase, in the absence of cholestasis or hemolysis	
Combined elevations of AST or ALT and total bilirubin:
 
After discontinuing the participant from capmatinib permanently, repeat LFTs as soon as possible, preferably within 48 hr from awareness of the abnormal results, then with weekly monitoring of LFTs, or more frequently if clinically indicated, until AST, ALT, or bilirubin have resolved to baseline or stabilization over 4 weeks.
 
Core LFTs consist of ALT, AST, GGT, total bilirubin (fractionated [direct and indirect], if total bilirubin $> 2.0 \times$ ULN), and alkaline phosphatase (fractionated [quantification of isoforms], if alkaline phosphatase $> 2.0 \times$ ULN.)

METABOLIC	
Asymptomatic amylase or lipase \geq CTCAE grade 3	
Test weekly (or more frequently) until \leq CTCAE grade 2.
 
A CT scan or equivalent imaging procedure to assess the pancreas, liver, and gallbladder is recommended within 7 days of the first occurrence of any \geq CTCAE grade 3 result, to exclude disease progression or potential other liver or pancreatic disease.

CARDIAC	
\geq CTCAE grade 3	Test weekly (or more frequently) until \leq CTCAE grade 2.
QTcF \geq 501 ms (CTCAE grade 3)	
When QTcF \geq 501 ms (CTCAE grade 3), perform the following:
 
Perform an analysis of serum potassium, calcium, phosphorus, and magnesium, and if below lower limit of normal, correct with supplements to within normal limits.
 
Review concomitant medication usage for the potential to prolong the QT-interval.
 
Check compliance with correct dose and administration of capmatinib.
 
Perform a repeat ECG within one hour of the first QTcF of \geq 501 ms.
 
If QTcF remains \geq 501 ms, repeat ECG as clinically indicated, but at least once daily until the QTcF returns to < 501 ms.
 
Repeat ECGs 7 days and 14 days (and then every 21 days) after dose resumption for all participants who had therapy interrupted due to QTcF \geq 501 ms.
 
If QTcF of \geq 501 ms recurs, repeat ECGs as described above.
 
Notes:
 
Call the study's central ECG review laboratory immediately and request an immediate manual read of the ECG”

TOXICITY	FOLLOW-UP EVALUATION
	The investigator should contact the Novartis Medical Lead or designee regarding any questions that arise if a participant with QTcF prolongation should be maintained on study.
GASTROINTESTINAL	
Diarrhea	
Investigate potential concomitant medication, food or comorbidity driven causes of diarrhea (including infectious causes) and remedy these causes if possible (e.g. discontinuation of concomitant medication, dietary modification, treatment of comorbidity).

	
The participant should be monitored for signs of dehydration and instructed to take preventive measures against dehydration as soon as diarrhea occurs. Antidiarrheal medication must be initiated at the first sign of abdominal cramping, loose stools or overt diarrhea. Concomitant medication for the treatment of diarrhea should follow local practice and the investigator's best judgment and may follow "the recommended guidelines for the treatment of cancer treatment-induced diarrhea" (Benson et al 2004). For example:
 
For uncomplicated diarrhea (grade 1 or 2 without complicating signs or symptoms), loperamide given at a standard dose (e.g. initial administration of 4 mg, then 2 mg every 2-4 hr, maximum of 16 mg/day), along with oral hydration and dietetic measures should be considered. Note: complicating signs or symptoms include moderate to severe cramping, decreased performance status, fever, neutropenia, frank bleeding or dehydration.
 
For complicated diarrhea (all grade 3 or 4, grade 1-2 with complicating signs or symptoms), management should involve intravenous (IV) fluids, and consider treatment with octreotide (at starting dose of 100 to 150 µg sub-cutaneous tid or 25 to 50 µg IV) and antibiotics (e.g. fluoroquinolone) should be given

Nausea and Vomiting	
The investigator should consider/investigate potential concomitant medication, food or comorbidity driven causes of nausea and/or vomiting and remedy these causes if possible (e.g. discontinuation of concomitant medication, dietary modification, treatment of comorbidity).
 
Individualized supportive and anti-emetic treatment should be initiated, as appropriate, at the first signs and/or symptoms of these AEs. In participants with vomiting, the participant should be monitored for signs of dehydration and instructed to take preventive measures against dehydration.
 
Concomitant medication for the treatment of nausea and/or vomiting should follow local practice and the investigator's best judgment.

SKIN TOXICITY	
Rash and Photosensitivity	

TOXICITY	FOLLOW-UP EVALUATION
CTCAE grade 1	Consider to initiate appropriate skin toxicity therapy (such as antihistamines, topical corticosteroids and low-dose systemic corticosteroids)
CTCAE grade 2	Initiate/intensify appropriate skin toxicity therapy (such as antihistamines, topical corticosteroids and low-dose systemic corticosteroids).
≥ CTCAE grade 3	Intensify appropriate skin toxicity therapy and monitor weekly or more frequently until resolved to grade ≤ 2
Peripheral edema	
CTCAE grade≤2	Consider to initiate conservative measures such as leg elevation, compression stockings, and dietary salt modification as clinically indicated.
CTCAE grade≥3	Initiate/intensify conservative measures
RESPIRATORY, THORACIC AND MEDIASTINAL DISORDERS	
ILD/Pneumonitis	
CTCAE Grade 1	
CT scan (high-resolution with lung windows) recommended, with serial imaging to monitor for resolution or progression- re-image at least every 3 weeks
 
Monitor for symptoms every 2-3 days - Clinical evaluation and laboratory work-up for infection
 
Monitoring of oxygenation via pulse oximetry recommended
 
Consultation of pulmonologist recommended

CTCAE Grade 2	
CT scan (high-resolution with lung windows)
 
 Monitor symptoms daily, consider hospitalization Clinical evaluation and laboratory work up for infection Consult pulmonologist Pulmonary function tests a - if normal at baseline, repeat every 8 weeks Bronchoscopy with biopsy and/or BAL recommended ^c 
Symptomatic therapy including corticosteroids if clinically indicated (1 to 2 mg/kg/day prednisone or equivalent as clinically indicated) b

CTCAE Grade 3 and Grade 4	
CT scan (high-resolution with lung windows)
 
Clinical evaluation and laboratory work-up for infection
 
Consult pulmonologist
 
Pulmonary function testsa-if < normal, repeat every 8 weeks until ≥ normal
 
Bronchoscopy with biopsy and/or BAL if possible^c
 
Treat with IV steroids (methylprednisolone 125 mg) as indicated. When symptoms improve to ≤ Grade 1, a high dose oral steroid

TOXICITY	FOLLOW-UP EVALUATION
	
(prednisone 1 to 2 mg/kg once per day or dexamethasone 4 mg every 4 hr)b.
 
If IV steroids followed by high dose oral steroids does not reduce initial symptoms within 48 to 72 hours, consider non-corticosteroid immunosuppressive medication

^a PFT (Pulmonary function tests) to include: diffusing capacity corrected for hemoglobin (DLCO); spirometry; resting oxygen saturation

Guideline for significant deterioration in lung function: Decrease in spirometry and/or DLCO of 30% and/or O₂ saturation \leq 88% at rest on room air.

b Duration and dose of course of corticosteroids will vary according to circumstances but should be as limited as possible. Consider tapering dosage at end.

c If bronchoscopy is performed, bronchoalveolar lavage (BAL) should be done where possible to exclude alveolar hemorrhage, opportunistic infections, cell count + determination lymphocyte CD4/8 count where possible.

Follow-up on potential drug-induced liver injury (DILI) cases

Participants with transaminase increase combined with total bilirubin increase may be indicative of potentially severe drug- induced liver injury (DILI) and should be considered as clinically important events and assessed appropriately to establish the diagnosis. The required clinical information, as detailed below, should be sought to obtain the medical diagnosis of the most likely cause of the observed laboratory abnormalities.

The threshold for potential DILI may depend on the participant's baseline AST/ALT and total bilirubin value; participants meeting any of the following criteria will require further follow-up as outlined below:

- For participants with normal ALT and AST and total bilirubin value at baseline: AST or ALT $>$ 3.0 x ULN combined with total bilirubin $>$ 2.0 x ULN
- For participants with elevated AST or ALT or total bilirubin value at baseline: [AST or ALT $>$ 3.0 x baseline] OR [ALT or AST $>$ 8.0 x ULN], whichever is lower, combined with [total bilirubin $>$ 2.0 x baseline AND $>$ 2.0 x ULN]

As DILI is essentially a diagnosis of exclusion, other causes of abnormal liver tests should be considered and their role clarified before DILI is assumed as the cause of liver injury.

A detailed history, including relevant information such as review of ethanol consumption, concomitant medications, herbal remedies, supplement consumption, history of any pre-existing liver conditions or risk factors, should be collected.

Laboratory tests should include ALT, AST, total bilirubin, direct and indirect bilirubin, GGT, GLDH, prothrombin time (PT)/ International normalized ratio (INR), alkaline phosphatase, albumin, and creatine kinase.

Evaluate status of liver metastases (new or exacerbation) or vascular occlusion – e.g. using CT, MRI, or duplex sonography.

Perform relevant examinations (Ultrasound or MRI, ERCP) as appropriate, to rule out an extrahepatic cause of cholestasis. Cholestasis (is defined as an ALP elevation $>$ 2.0 x ULN with R value $<$ 2 in participants without bone metastases, or elevation of the liver-specific ALP isoenzyme in participants with bone metastases).

Note: The R value is calculated by dividing the ALT by the ALP, using multiples of the ULN for both values. It denotes whether the relative pattern of ALT and/or ALP elevation is due to cholestatic ($R \leq 2$), hepatocellular ($R \geq 5$), or mixed ($R > 2$ and < 5) liver injury. In clinical situations where it is suspected that ALP elevations are from an extrahepatic source, the GGT can be used if available. GGT may be less specific than ALP as a marker of cholestatic injury, since GGT can also be elevated by enzyme induction or by ethanol consumption. It is more sensitive than ALP for detecting bile duct injury (livertox.nih.gov/rucam.html).

Table 17 provides guidance on specific clinical and diagnostic assessments which can be performed to rule out possible alternative causes of observed LFT abnormalities.

Table 17. Clinical And Diagnostic Assessments for LFT Abnormalities

Disease	Assessment
Hepatitis A, B, C, E	IgM anti-HAV; HBsAg, IgM & IgG anti-HBc, HBV DNA; anti-HCV, HCV RNA, IgM & IgG anti-HEV, HEV RNA
CMV, HSV, EBV infection	IgM & IgG anti-CMV, IgM & IgG anti-HSV; IgM & IgG anti-EBV
Autoimmune hepatitis	ANA & ASMA titers, total IgM, IgG, IgE, IgA
Alcoholic hepatitis	Ethanol history, GGT, MCV, CD-transferrin
Nonalcoholic steatohepatitis	Ultrasound or MRI
Hypoxic/ischemic hepatopathy	Medical history: acute or chronic CHF, hypotension, hypoxia, hepatic venous occlusion. Ultrasound or MRI.
Biliary tract disease	Ultrasound or MRI, ERCP as appropriate.
Wilson disease (if <40 yrs old)	Ceruloplasmin
Hemochromatosis	Ferritin, transferrin
Alpha-1-antitrypsin deficiency	Alpha-1-antitrypsin

Other causes should also be considered based upon participants' medical history (hyperthyroidism / thyrotoxic hepatitis – T3, T4, TSH; CVD / ischemic hepatitis – ECG, prior hypotensive episodes; T1D / glycogenic hepatitis).

Obtain PK sample to determine exposure to study treatment and metabolites.

Following appropriate causality assessments, as outlined above, the causality of the treatment is estimated as “probable” i.e. $>50\%$ likely, if it appears greater than all other possible causes of liver injury combined. The term “treatment-induced” indicates *probably caused* by the treatment, not by something else, and only such a case can be considered a DILI case and should be reported as an SAE.

All cases confirmed on repeat testing meeting the laboratory criteria defined above, with no other alternative cause for LFT abnormalities identified, should be considered as “medically significant,” and thus, meet the definition of SAE and should be reported as SAE using the term “potential treatment-induced liver injury.” All events should be followed up with the outcome clearly documented.

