7.4 Dose Limiting Toxicity (DLT)

DLT is defined as any of the following possibly, probably, or definitely due to study therapy, assessed during the first 2 cycles [56 days]:

- Any death not clearly due to the underlying disease or extraneous causes
- Non- hematologic toxicity
 - Grade 3 or higher non-hematologic toxicity, Grade 3 diarrhea will be considered a DLT only if it lasts \geq 2 days despite prophylaxis and optimal standard medication and medical management.

- Grade 2 diarrhea lasting \geq 5 days despite prophylaxis and optimal standard medical management
- Pulmonary toxicity
 - Any grade of pneumonitis or ILD confirmed not attributable to infection or another etiology.
- Hy's Law case, defined as a patient meeting all of the following criteria:
 - ALT or AST \geq 3 x Upper Limit of Normal (ULN)
 - Total bilirubin >2 x ULN
 - Little or no evidence of cholestasis (alkaline phosphatase <2 x ULN)
 - No other identified explanation for the injury (such as hepatitis A, B, C, or other viral hepatic injury, alcohol ingestion, congestive heart failure).
- Neutropenic fever, defined as per CTCAE version 5.0:
ANC $<1000/\text{mm}^3$ and a single temperature of >38.3 degrees C (101 degrees F) or a sustained temperature of $>=38$ degrees C (100.4 degrees F) for more than one hour.
- Hematologic toxicity
 - Grade 4 neutropenia or thrombocytopenia >7 days
 - Grade 3 thrombocytopenia with bleeding
 - Grade 4 anemia

The targeted maximum DLT rate is 25%, and we will enroll patients in cohorts of size 3.

Table 4. Capmatinib and Neratinib overlapping toxicities

SOC	Capmatinib toxicity (Ref: CDS)	Neratinib toxicity (Ref: USPI and SmPC)
Congenital, familial and genetic disorders	Embryo-Fetal Toxicity	Embryo-Fetal Toxicity
Gastrointestinal disorders	Diarrhoea	Diarrhoea
	Vomiting	Vomiting
	Nausea	Nausea
	Constipation	Abdominal pain*
	Amylase increased	Stomatitis**
	Lipase increased	Dyspepsia
	Acute pancreatitis	Abdominal distension
		Dry mouth

General disorders and administration site conditions	Fatigue ¹	Fatigue
	Weight decreased	Weight decreased
	Back pain	
	Oedema peripheral ²	
	Non-cardiac chest pain ³	
	Pyrexia ⁴	
Hepatobiliary disorders	Alanine aminotransferase increased	Alanine aminotransferase increased
	Aspartate aminotransferase increased	Aspartate aminotransferase increased
	Blood bilirubin increased	Blood bilirubin increased

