12.2 Serious Adverse Event Reporting (SAE)

12.2.1 Internal SAE reporting to Investigational New Drug (IND) Office

Serious Adverse Event (SAE) Reporting Requirements for M D Anderson Sponsor Single Site IND Protocols

An adverse event or suspected adverse reaction is considered “serious” if, in the view of either the investigator or the sponsor, it results in any of the following outcomes:

- Death
- A life-threatening adverse event
- Inpatient hospitalization or prolongation of existing hospitalization
- A persistent or significant incapacity or substantial disruption of the ability to conduct normal life functions.
- A congenital anomaly/birth defect.

Important medical events that may not result in death, be life-threatening, or require hospitalization may be considered a serious adverse drug experience when, based upon appropriate medical judgment, they may jeopardize the patient or subject and may require medical or surgical intervention to prevent one of the outcomes listed in this definition.

Examples of such medical events include allergic bronchospasm requiring intensive treatment in an emergency room or at home, blood dyscrasias or convulsions that do not result in inpatient hospitalization, or the development of drug dependency or drug abuse (21 CFR 312.32).

- Important medical events as defined above, may also be considered serious adverse events. Any important medical event can and should be reported as an SAE if deemed appropriate by the Principal Investigator or the IND Sponsor, IND Office.
- All events occurring during the conduct of a protocol and meeting the definition of a SAE must be reported to the IRB in accordance with the timeframes and procedures outlined in “The University of Texas M. D. Anderson Cancer Center Institutional Review Board Policy on Reporting Adverse Events for Drugs and Devices”.

- Serious adverse events will be captured from the time of the first protocol-specific intervention, until 30 days after the last dose, unless the participant withdraws consent.
- Serious adverse events must be followed until clinical recovery is complete and laboratory tests have returned to baseline, progression of the event has stabilized, or there has been acceptable resolution of the event.
- All SAEs, expected or unexpected/ initial or follow up, must be reported to the IND Office **within 5 working days of knowledge of the event** regardless of the attribution.

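### Section 10.5.3 gives two inconsistent SAE triggers for combined ALT/AST and bilirubin elevation, and the stricter one conflicts with Section 12.2, where SAEs are reported regardless of attribution

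*Combined protocol and SAP*

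**What the plan says.** Section 10.5.3 (follow-up on potential drug-induced liver injury) says that patients with a combined transaminase and bilirubin rise "should be considered as clinically important events and assessed appropriately to establish the diagnosis". It sets laboratory thresholds that depend on baseline values. Two paragraphs on reporting then close the section.

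- **The 50% paragraph.** After the causality work-up, treatment is the probable cause, meaning more than 50% likely, "if it appears greater than all other possible causes of liver injury combined". It then states: "only such a case can be considered a DILI case and should be reported as an SAE".
- **The laboratory paragraph.** "All cases confirmed on repeat testing meeting the laboratory criteria defined above, with no other alternative cause for LFT abnormalities identified" are to be treated as medically significant. They therefore "meet the definition of SAE and should be reported as SAE using the term" for potential treatment-induced liver injury. No probability threshold is set.

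Section 12.2.1 defines seriousness by outcome or by medical importance. It says "All SAEs, expected or unexpected/ initial or follow up, must be reported to the IND Office" within 5 working days of knowledge of the event, whatever the attribution. Section 12.2.3 asks for SAEs to go to both supplying companies within 24 working hours whatever the suspected causality, and its parenthesis names possibly related events. Section 12.1.2 lists Possible as a category separate from Probable. Section 7.4 sets the DLT threshold at the lower level: "DLT is defined as any of the following possibly, probably, or definitely due to study therapy".

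**The concern.** The two paragraphs cover the same event and can give opposite answers on whether it is an SAE. The first also makes causality a condition of being reported as an SAE, whereas Section 12.2 treats causality as something recorded about an SAE that is reported in any case. An investigator who follows the 50% paragraph literally would not send in a case rated possible.

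This matters because combined elevation is a serious hepatic signal in this protocol. Without cholestasis or hemolysis, Table 15 makes permanent discontinuation of capmatinib mandatory. Section 8.2.2 advises caution when capmatinib is given with other anticancer drugs of known hepatotoxic risk, and Table 6 shows raised ALT in 8.5% of patients on neratinib alone. Expedited SAE reporting is the prompt route by which the IND Office and the suppliers would learn of a case.

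**Working it through.** The plan states no figure here to reproduce, so the check sets the rules side by side. Every case below meets the Section 10.5.3 laboratory criteria on repeat testing. Cases A to D have no other seriousness outcome. I assume that a rating of Possible on the Section 12.1.2 scale means treatment is not more than 50% likely; Section 10.5.3 does not itself refer to that scale.

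| Case | 50% paragraph | Laboratory paragraph | Section 12.2.1 |
|---|---|---|---|
| A. No alternative cause; treatment more than 50% likely | SAE | SAE | SAE if judged an important medical event; attribution plays no part |
| B. No alternative cause; treatment rated possible | Not an SAE | SAE | As A |
| C. Competing cause named; treatment still more than 50% likely | SAE | Not covered | As A |
| D. Competing cause named; treatment rated possible | Not an SAE | Not covered | As A |
| E. Hospitalised, life-threatening or fatal; treatment rated possible | Not an SAE if read literally | Depends on whether another cause is found | SAE |

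B is a direct contradiction within Section 10.5.3. C and D show that neither paragraph contains the other. E shows that the 50% paragraph, read literally, conflicts with Section 12.2.1.

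**What else would pick up cases B and D.** Section 12.1.4 makes a laboratory abnormality an adverse event if it leads to a dose change, interruption or discontinuation. Under the monitoring rules in Section 13.2, toxicity summaries go to the IND Office after every 3 evaluable patients in Phase Ib and every 6 in Phase II, once those patients complete 56 days. These routes exist but are slower than SAE reporting. They may also carry less weight. For example, ALT of 4 x ULN with bilirubin of 2.5 x ULN, from normal baseline, meets the Section 10.5.3 criteria, yet each value is Grade 2 on the Table 15 scale. On those grades the case would not count toward the Phase II stopping rule for Grade 3 or higher toxicity.

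**Timing.** The Section 12.2.1 clock starts at knowledge of the event. The Section 10.5.3 triggers follow a repeat test (Table 16: preferably within 48 hours) and a search for other causes that has no stated deadline.

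**Size.** The documents give no rate of combined elevations. If the rate were 1% to 2% (an assumption), the chance of at least one among 47 patients would be 1 - 0.99^47 = 0.376 to 1 - 0.98^47 = 0.613. The nearest documented figure is raised bilirubin of any kind on neratinib alone: 4 of 1408 (Table 6), which gives 1 - (1 - 4/1408)^47 = 0.125. That comes from early-stage patients on a single drug and does not transfer directly.

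**The case against.** The best defence is that the sections do different jobs. Section 12.2.1 says what to do with an event once it is an SAE; a laboratory elevation alone is not on its outcome list. Section 10.5.3 adds a route to SAE status and does not say that it overrides Section 12. The word *only* can also be read as attaching to the label DILI, since the laboratory paragraph uses a different term. And because DILI is a diagnosis of exclusion, a case with no other cause found will usually be judged more than 50% likely, so the two paragraphs mostly agree.

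Much of this stands. It confines the direct contradiction to case B and makes a lenient reading possible. It does not remove the problem: a safety-reporting rule should not depend on which reading the investigator chooses.

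A reader might infer four stronger things that the documents do not support.

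- **That hospitalised, life-threatening or fatal cases go unreported.** They are SAEs under Section 12.2.1, as is any important medical event that the principal investigator or IND sponsor considers reportable.
- **That a Hy's Law DLT escapes SAE reporting.** Section 7.4 already requires that no other explanation be identified. In a patient with normal baseline liver tests, such a case is essentially what the laboratory paragraph makes an SAE once confirmed. If liver metastases are named as the cause, it is no longer a Hy's Law case under Section 7.4.
- **That the IND Office would not hear of these cases at all.** Adverse-event capture and the toxicity summaries still reach it, and Section 4.1 requires its review before dose levels change.
- **That reports will be late.** This is inferred from the order of steps. No text permits delay once an SAE is known, and a repeat test within 48 hours would normally fit inside 5 working days.

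**Conclusion.** The inconsistency is real and rests on the text alone. Section 10.5.3 contains two SAE triggers that disagree for a confirmed case with no other cause and treatment rated possible. Read literally, the 50% paragraph also conflicts with Sections 12.2.1 and 12.2.3.

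Its reach is limited: mainly laboratory-defined cases with no other seriousness outcome and treatment rated only possible. What they could miss is expedited SAE reporting, not recording altogether.

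The size cannot be given from the documents. It is tempting to quote 38% to 61% as the chance that the defect bites. That range is the chance of any combined elevation at an assumed rate. Cases in the gap are only some of those, so at the same assumed rate the relevant chance is lower by an unknown amount. The conclusion does not depend on it.

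**What to change.** In Section 10.5.3:

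1. Delete the closing clause on SAE reporting from the 50% sentence, so that it governs only the label DILI.
2. Keep the laboratory paragraph as the laboratory-based SAE trigger.
3. Add a sentence stating that SAE status and reporting clocks follow Sections 12.2.1 and 12.2.3 regardless of attribution. Any case that meets an SAE outcome or is judged an important medical event is then reported from knowledge of the event, with causality recorded on the Section 12.1.2 scale and updated by follow-up report.

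Step 1 removes the only automatic trigger for case C, which would then depend on the medical-importance judgement. The sponsor should therefore decide in the same amendment whether cases with a named competing cause (C and D) are automatic SAEs. That is a genuine trade-off: including them would make hepatic progression that meets the thresholds an expedited SAE. The documents do not settle it, and the inconsistency can be repaired without dropping either repeat confirmation or the condition that no alternative cause is identified.

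The cost is one paragraph of wording and a few more SAE reports. Dosing, sample size and the statistical design do not change.
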